### 11.3. Not Reportable Events

Examples of events that are not reportable as adverse events for this study are:

- Inability to successfully perform the procedure, unless injury occurs.
- Lack of pain relief or a return to baseline pain level (change in pain will be assessed as the efficacy objective).
- A documented pre-existing condition unless there is a worsening of the nature, severity, duration, or frequency of that condition if it meets the defined criteria in Section 11.2.
- Planned medical or surgical procedures (e.g., surgery, endoscopy, tooth extraction, transfusion, cosmetic elective surgery); however, the condition leading to the procedures might be a reportable event if it meets the defined criteria in Section 11.2.

Table 11-3 provides a list of expected surgical adverse events. An expected surgical event will not be considered reportable unless it worsens or is present outside the stated timeframe post-procedure.

Time frame after the surgical procedure

Anesthesia-related nausea/vomiting 24 hours

Low-grade fever (<100°F or < 37.8°C) 48 hours

Mild to moderate bruising / ecchymosis 7 days

Seroma 72 hours

Sleep problems (insomnia) 72 hours

**Table 11-3: Expected Surgical Adverse Events and Durations** 

#### 11.4. Device Deficiencies

A device deficiency (DD) is an inadequacy of a medical device with respect to its identity, quality, durability, reliability, safety or performance. Device deficiencies include malfunctions, misuse or use errors, and inadequate labeling. All device deficiencies must be documented and submitted to Medtronic on the Device Deficiency eCRF. In addition, the Investigator must also determine and document on the eCRF device deficiencies that did not lead to adverse event but could have led to a serious adverse device effect:

- if either suitable action had not been taken,
- if intervention had not been made, or
- if circumstances had been less fortunate
- Refer to Table 14-1 for Investigator reporting timelines for device deficiencies.

#MDT16075 Version 4.0

Page 53 of 81

# 11.5. Reporting Serious Adverse Device Effects, and Device Deficiencies to Medtronic

Reporting timelines can be found in Table 14-1. If necessary, the Investigator may report the event to Medtronic or its designee initially by telephone or email and follow-up with completed Adverse Event and/or Device Deficiency eCRFs and, if possible, copies of source documentation regarding the event (e.g., physician/nurse notes or summaries) should also be provided to Medtronic.

#### 11.6. Deaths

All subject deaths must be reported to Medtronic and the IRB/EC as soon as possible, but **no more than 5 working days** after learning of a subject's death, regardless of whether or not the death is related to the device system or therapy. The Investigator should also attempt to determine, as conclusively as possible, whether such deaths are related to the device system, therapy, and/or procedure. If the death is evaluated as device, therapy and/or procedure related and unanticipated, the event will be reported as a USADE by Medtronic or its designee to the appropriate regulatory agencies.

The principal investigator should provide as much of the following supporting documentation as possible for deaths:

- Death certificate
- Death summary/hospital records, if allowed by state/local law
- Autopsy report, if allowed by state/local law

All device system components that were being used at the time of the death should be returned to Medtronic for analysis, if applicable. Any subject death related to the device/procedure and/or therapy will be reported on the Adverse Event and Study Exit eCRFs. If limited information is known, the Study Exit eCRF must be completed with available information as soon as possible. As information becomes available, the Study Exit eCRF will be updated and/or an Adverse Event eCRF may be required if the death was later determined to be related to the device, procedure and/or therapy. If the death occurs at a location remote from the study site, it is the study site's responsibility to make every attempt to retrieve all pertinent information related to the subject's death and submit the investigator's death summary of the known events surrounding the death to Medtronic or its designee.

#### 12. Data Review Committees

This study will utilize an independent Clinical Events Committee (CEC) to adjudicate deaths to determine the relationship of the death to the device, procedure and/or therapy.

#MDT16075 Version 4.0

Page 54 of 81

Medtronic

The CEC may request clarification and/or additional information from the principal investigator who reported the event. If the conclusion of the review differs from the principal investigator's assessment, both opinions will be reported back to the investigator and noted in the final study report.

### 13. Statistical Design and Methods

### 13.1. General Statistical Considerations

Data analysis will be performed by Medtronic-employed statisticians or designees. A validated statistical software package (e.g., SAS version 9.4 or higher) will be used to analyze the study results.

The Statistical Analysis Plan (SAP) will be developed prior to data analysis and will include a comprehensive description of the statistical methods and reports to be included in the final study report. Any change to the data analysis methods described in the CIP will require an amendment only if it changes a principal feature of the CIP. Any other change to the data analysis methods described in the CIP, and the justification for making the change, will be described in the clinical study report.

#### 13.1.1. Study Sample Size Justification

The sample size calculations were performed using PASS 11 statistical software. (PASS 11 v. 11.0.7, Hintze J). Details of the sample size calculations are provided in the primary objective section.

The primary objective is to demonstrate an improvement from baseline to 3 months post radiofrequency ablation in worst pain score in the past 24 hours in subjects treated for metastatic lesions involving only the vertebral body. A sample size of 35 subjects successfully treated and completing the pain assessment at 3 months is expected to provide results that will be considered relevant to clinicians, as well as provide acceptable power to test the primary objective. After accounting for the attrition from treatment through the pain assessment at 3 months, 52 subjects are required to be treated with the OsteoCoolTM RF Ablation system.

Sample size requirements will only be calculated for the primary objective. There are no sample size requirements for the secondary objective and the additional objectives.

#### **Enrollment Sample Size**

The study size will be 250 enrolled subjects. The goal is 100 with metastatic lesions involving only the vertebral body, 100 with metastatic lesions outside the vertebral body, and 50 with benign bone tumors. The increased sample size will allow for richer safety reporting and long-term follow-up.

#### 13.1.2. Description of Baseline Variables

Baseline variables representing subject clinical characteristics will be presented.

#### 13.1.3. Center Pooling

Throughout the study, efforts will be made to ensure consistency among investigative centers in selection of subjects and conduct of the study procedures. Training on the protocol and programming

#MDT16075 Version 4.0

Page 55 of 81

procedures will be done for all sponsor and center staff involved in this study. Center monitoring will also help ensure consistency.

Due to the relatively small number of subjects expected at each center, there is no plan to use statistical methods to test for a difference among centers. There is no a priori plan to analyze the primary and secondary objectives by study center.

There is no a priori plan to exclude any centers from the analysis.

For the overall study size of 250, each center can contribute no more than 50 subjects (from both subject cohorts combined) without prior Medtronic approval.

#### 13.1.4. Special Considerations

#### **Subject Cohorts**

There will be two subject cohorts, which will be used to separate the subjects to be analyzed in the primary objective versus the secondary objective.

Primary objective cohort: subjects with metastatic lesions involving the vertebral body only

**Secondary objectives cohort:** subjects with metastatic lesions and benign bone tumors outside the vertebral body. This includes subjects with a combination of lesions involving the vertebral body and outside the vertebral body. This cohort may get divided further depending on treatment site (for example: non-vertebral bone, benign bone tumors, combinations).

At the time of treatment with the OsteoCool™ RF Ablation system, subjects will get assigned to one of the two cohorts depending on the lesion type(s) treated. The two cohorts encompass the entire set of treated subjects, and are mutually exclusive.

#### **Analysis Populations**

There are 3 analysis populations:

The *Enrolled* will include all enrolled subjects and will be used in the safety measures.

The populations of study subjects to be included in the efficacy analyses (primary objective, secondary objective, and additional measures) are described below.

**Treated:** The Treated population will be defined as all subjects who are successfully treated with the OsteoCool™ RF Ablation system. This is similar to a Full Analysis Set.

**Completers:** The Completers population will be defined as the subset of **Treated** subjects who provided endpoint data at the 3-Month Visit. The Completers population will be a subset of the Treated population. The Completers population will be the analysis population for the primary objective hypothesis testing.

#### **Missing Endpoint Data**

Study centers will be instructed to make every effort to keep subjects actively attending study visits. The primary and secondary objective assessments are planned to be collected at the 3-Month follow-up

#MDT16075 Version 4.0 Page 56 of 81

visit. If subjects miss their scheduled 3-Month follow-up visit, the investigator will attempt to collect the data within the visit window or before study discontinuation. Phone calls may also be utilized to obtain data for the primary endpoint.

Completers population: The Completers population will be analyzed without imputations for missing data. (By definition, the endpoint data was provided.) It is assumed that the primary reasons for missing endpoint data will be death or inability to contact subjects due to deteriorating health (Bagla) and not related to pain score level. Thus, inclusion in the Completers population is assumed to not be confounded with endpoint pain score level.

Sensitivity Analysis: The Treated population is expected to have missing endpoint data. The frequency, timing, and reasons for missing data will be reported and analyzed to assess potential for bias. Sensitivity analyses of the primary objective, detailed in the primary objective analysis methods section below, will include analyzing the Treated population using multiple imputation and single imputation. The results of these analyses may suggest other specific sensitivity analyses or imputation strategies.

#### **Adjustments for Multiple Endpoints**

The primary objective will be tested at a two-sided alpha level of 0.05. There are no hypothesis tests associated with the secondary objective or additional measures, so no adjustment for multiple endpoints is required.

#### 13.1.5. Interim analyses

There will be no formal interim statistical analyses.

#### **13.1.6.** Reports

Annual reports of study progress and safety data will be provided. The primary objective hypothesis will be tested and reported after the sample size requirements for it have been met, and a final study report will be prepared once final study data is collected.

#### 13.2. Demographics

Demographic characteristics and baseline cancer and pain history will be summarized for all enrolled and treated subjects.

### 13.3. Primary Objective

#### 13.3.1. Primary objective

To demonstrate an improvement from baseline to 3 months post radiofrequency ablation in worst pain score in the past 24 hours in subjects treated for metastatic lesions in only the thoracic and/or lumbar vertebral body(ies)

### 13.3.2. Hypothesis

 $H_0$ :  $\mu_c = 0$ 

#MDT16075 Version 4.0

Page 57 of 81

 $H_A$ :  $\mu_c \neq 0$ 

Where  $\mu_c$  is the mean change from baseline to the 3-Month Visit in worst-pain score.

#### 13.3.3. Data Collection

At the baseline and 3-Month study visits, the worst pain question in the BPI will be used to evaluate the pain severity:

Please rate your pain by circling the one number that best describes your pain at its worst in the last 24 hours (circle only one number, 0-10). No pain = 0, Pain as bad as you can imagine = 10

#### 13.3.4. Endpoint Definition

Change in pain will be calculated as:

 $\mu_c$  = worst-pain 3-month – worst-pain baseline

A negative value for change in pain represents a lowering of the subject's pain score (an improvement, or reduction in pain) and a positive value represents an increase in the subject's pain score (a worsening, or increase in pain).

#### 13.3.5. Sample Size Methods and Assumptions

The standard deviation of change from Greenwood et al (2015) is estimated to be 4.1 at 4 weeks. The standard deviation of change in the CAFE study Berenson et al (2011) was 3.2 at 1 month. The standard deviation of change from Lane et al (2011) is estimated to be 2.4 at 1 day post-procedure. It is not known which of those studies will most closely match the population and test conditions in this study. The median of those 3 studies is 3.2. To account for this study having a longer follow-up period and a more diverse patient population, and thus more opportunity for variability, the standard deviation for our sample size calculation will be increased to 3.5.

The minimal clinically important difference (MCID) of 2 points was used to interpret pain score differences in terms of clinical relevance in Bagla et al (2016) and a clinically significant change in pain of 2 points was also identified in Greenwood. This will be used for our calculations.

Bagla followed subjects for 3 months post procedure. They reported that pain scores were provided for 68% of subjects (32% not provided) at 3 months. This will be used for our calculations.

The PASS program used to calculate the sample size was the one-sample t-test power analysis, mean0=0, meanA=2, standard deviation (of change) =3.5, two-sided significance level (alpha)=0.05, and power=0.90. The required sample size was 35. To account for subjects getting treated but not providing the 3-Month data, the treated sample size is adjusted for a 32% loss, to 52.

#MDT16075 Version 4.0

Page 58 of 81

#### 13.3.6. Analysis Methods

A two-sided t-test with alpha=0.05 will be used to test the null hypothesis of no change in worst-pain score between baseline and 3 months.

If the distribution of the change scores does not meet the assumption of normality, the non-parametric Wilcoxon signed-rank test will be used to test for significant change with alpha=0.05, two-sided.

The primary objective hypothesis will be tested after the sample size requirements for it have been met. If additional subjects are enrolled later and also treated for metastatic lesions involving only the vertebral body, those additional subjects will be combined with the first group and summarized together.

The main analysis for the primary objective hypothesis testing will be on the Completers population.

In order to include all the treated subjects in the analysis, a sensitivity analysis will be performed on the Treated population. The endpoint data will first undergo multiple imputations (MI). Rather than filling in a single value for each missing value, MI replaces each missing value with a set of "plausible" values that represent the uncertainty about the correct value to impute. These multiple imputed datasets are then analyzed using standard statistical procedures and then combined into one analysis result with an appropriately increased variance. Included in the MI analysis will be the endpoint variable at 3 months and the endpoint variable at baseline, 3 days, 1 week, 1 month, and unscheduled visits (if collected), as well as baseline covariates. The method to be used is the Markov chain Monte Carlo (MCMC) method of SAS (version 9.4 or higher). This is an iterative method that can be used when the pattern of missing data is arbitrary (monotone or non-monotone). The default number of iterations will be used (n=5) and, if needed, will be increased until the Markov chain converges.

A single imputation method will also be performed, substituting the Treated population's endpoint variable at the last available follow-up (Bagla) for the missing endpoint variable.

Sensitivity analyses will be performed, separating the evaluation by whether or not the subjects received vertebral augmentation procedures and/or post RFA radiation therapy.

### 13.4. Secondary Objective

The data collection and endpoint definition for the secondary objective will be the same as for the primary objective.

#### 13.4.1. Secondary objective

To characterize change from baseline to 3 months post radiofrequency ablation in worst pain score in the past 24 hours in subjects treated for metastatic lesions in the periacetabulum, iliac crest, and/or sacrum, and for benign bone tumors

#### 13.4.2. Hypothesis

There is no formal hypothesis. The objective is to characterize the change in pain.

#MDT16075 Version 4.0 Page 59 of 81

#### 13.4.3. Data Collection

At the baseline and 3-Month study visits, the worst pain question in the BPI will be used to evaluate the pain severity:

Please rate your pain by circling the one number that best describes your pain at its worst in the last 24 hours (circle only one number, 0-10). No pain = 0, Pain as bad as you can imagine = 10.

#### 13.4.4. Endpoint Definition

Change in pain will be calculated as:

 $\mu_c$  = worst-pain 3-month - worst-pain baseline

A negative value for change in pain represents a lowering of the subject's pain score (an improvement, or reduction in pain) and a positive value represents an increase in the subject's pain score (a worsening, or increase in pain).

#### 13.4.5. Sample Size Methods and Assumptions

There are no sample size requirements or calculations for the secondary objective.

#### 13.4.6. Analysis Methods

The Treated and Completers populations will both be reported on.

Descriptive statistics, as well as confidence intervals, of the change in pain will be reported.

The subsets of subjects in the secondary objective cohort (subjects with metastatic lesions outside the vertebral body and/or benign bone tumors) will be reported on as a whole, and also individually (metastatic lesions outside the vertebral body, benign bone tumors, and combinations which may also include metastatic lesions involving the vertebral body.)

### 13.5. Safety Measure

Characterize incidence of all device, procedure and/or therapy related adverse events and device deficiencies from enrollment to the 12-Month Visit.

#### 13.5.1. Data Collection and Endpoint Definitions

Reported adverse events and device deficiencies will be collected on eCRFs. They will be coded and summarized using the Medical Dictionary for Regulatory Affairs (MedDRA). They will also be categorized by relationship to the device, procedure, or therapy.

Adverse events that occur concurrently to device deficiencies will be reported using the adverse event system.

#### 13.5.2. Analysis Methods

The Enrolled subjects will be included in the safety measures. Analyses of deaths will be presented using the final CEC determination.

#MDT16075 Version 4.0

Page 60 of 81

Medtronic

Device, therapy, and/or procedure related events will be presented separately from SAEs that are not related. Adverse events will be presented in summary tables displaying the number of serious events, the number of events, the number of subjects with  $\geq 1$  event, and the percentage of subjects with  $\geq 1$  event. The events will be presented by system organ class (SOC) and preferred term (PT). The events will also be presented sorted in descending order of frequency overall. Adverse event tables will be displayed by study phase where applicable. Adverse events may be reported using the classification system used by the Society of Interventional Radiology.

Device deficiencies will be presented in summary tables similar to adverse events.

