#### **Analysis Methods**

Revision 1.0

Page 12 of 15

The main analysis for the secondary objective will be on the Secondary Objective Cohort and will use the Completers Analysis Set.

Descriptive statistics, as well as confidence intervals, of the change in pain will be reported.

Missing data imputation and sensitivity analysis using the Treated Analysis Set will be performed similar to the primary objective methods described in Section 0.

The subsets of subjects in the Secondary Objective Cohort (subjects with metastatic lesions outside the vertebral body and/or benign bone tumors) will be reported on as a whole, and also individually (metastatic lesions outside the vertebral body, benign bone tumors, and combinations of differing lesion types.)

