### **Analysis Methods**

The Treated Analysis Set will be included in the safety measures. Since adverse events were only reportable if they were related to the device, therapy and/or procedure, by definition no adverse events could occur prior to the RFA procedure. Therefore, there is no need to include the enrolled subjects not receiving the RFA procedure.

Adverse events will be presented in summary tables displaying the number of serious events, the number of events, the number of subjects with ≥1 event, and the percentage of subjects with ≥1 event. The events will be presented by MedDRA system organ class (SOC) and MedDRA preferred term (PT). The events will also be presented sorted in descending order of frequency overall. Adverse event tables will be displayed by study phase where applicable. Adverse events will be presented in aggregate as well as separated out by relationship to device, therapy and/or procedure. The analyses will also be

Revision 1.0

Page 14 of 15

presented by objective cohort. Adverse events may be reported using the classification system used by the Society of Interventional Radiology.

Subject exposure will be characterized. If many subjects discontinue prematurely, the event rates may be adjusted by follow-up time.

Analyses of deaths will be presented using the final CEC determination. Any difference between CEC determination and investigator reporting will be noted in the reports.

Device deficiencies will be presented in summary tables similar to adverse events.

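### Planned safety tables go no finer than the two objective cohorts, so non-vertebral metastatic and benign-tumour subjects share one event rate

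*Combined protocol and SAP*

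**What the plan says.** **Safety tables.** CIP 13.5.2 sets out the content: "Adverse events will be presented in summary tables displaying the number of serious events, the number of events, the number of subjects with" at least one event, and the matching percentage, by system organ class and preferred term. The only other breakdown of subjects' experience there is by time: "Adverse event tables will be displayed by study phase where applicable". No cohort or lesion group is named. SAP 7.10 repeats the content and goes further: "Adverse events will be presented in aggregate as well as separated out by relationship to device, therapy and/or procedure". It adds that the analyses will also be "presented by objective cohort". Both documents give device deficiencies similar tables.

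**What a cohort contains.** SAP 7.1.3 defines two mutually exclusive cohorts. The Primary Objective Cohort is vertebral-only metastatic disease. The Secondary Objective Cohort takes everyone else who is treated: non-vertebral metastases, benign tumours, and combinations. CIP 13.1.4 and SAP 7.1.3 both allow this cohort to be divided further, but as an option, and neither safety section takes it up.

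**Enrolment.** CIP 13.1.1 and SAP section 6 set goals of 100 vertebral-only subjects, "100 with metastatic lesions outside the vertebral body, and 50 with benign bone tumors", and justify the enlarged study partly by fuller safety reporting.

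**Pain, for comparison.** CIP 13.4.6 commits to the lesion groups for the secondary pain result: they "will be reported on as a whole, and also individually (metastatic lesions outside the vertebral body, benign bone tumors, and combinations" that may include vertebral lesions. SAP 7.9.2 makes the same commitment.

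**The concern.** The study recruits three groups and sizes each with safety reporting in mind, yet only the vertebral-only group has a committed safety table of its own. The other two are joined under one denominator, although the labelled indications treat metastatic lesions and benign bone tumours as distinct uses.

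A percentage over the joined cohort is a weighted average whose weights are set by how many of each kind were recruited. Unless the two risks happen to be equal, it is the rate for neither group, and it would change with recruitment even if the device behaved identically. A clinician or regulator asking how often related events occur after ablation of a pelvic metastasis, or of a benign tumour, would have no planned table to consult.

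**Working it through.** **Inputs**

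- Enrolment goals (CIP 13.1.1, SAP section 6): 100 vertebral-only metastatic, 100 non-vertebral metastatic, 50 benign. Check: 100 + 100 + 50 = 250, the stated study size.
- Combination subjects belong to the secondary cohort, but no goal is given for them; taken as zero.
- The goals count enrolled subjects, while SAP 7.10 analyses treated subjects. The same treated fraction is assumed in each group, so the 2:1 mix is unchanged.
- Event risk by lesion group for this device: not in the documents. Let p_M be the non-vertebral metastatic risk and p_B = r × p_M the benign risk, with r assumed from 0 to 1.5.

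**Step 1, benign share of the secondary cohort.** 50 / (100 + 50) = 33%.

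**Step 2, pooled percentage.** (100 × p_M + 50 × r × p_M) / 150 = p_M × (2 + r) / 3.

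**Step 3, relative error.** Against the metastatic risk: (2 + r)/3 − 1 = (r − 1)/3, which does not depend on p_M. Against the benign risk: (2/3) × (1/r − 1).

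With p_M = 10% as an illustration:

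| r (assumed) | Benign risk | Pooled percentage | Error against metastatic | Error against benign |
|---|---|---|---|---|
| 0 | 0% | 6.7% | −33% | undefined |
| 0.25 | 2.5% | 7.5% | −25% | +200% |
| 0.5 | 5% | 8.3% | −17% | +67% |
| 1 | 10% | 10.0% | 0 | 0 |
| 1.5 | 15% | 11.7% | +17% | −22% |

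The sign changes at r = 1. The smaller benign group is misdescribed by more than the metastatic group.

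**Step 4, dependence on mix.** For a general benign share w the error against the metastatic risk is w × (r − 1). At r = 0.5 it is −10% if w is 20%, −17% at the planned 33%, and −25% if w is 50% (the 20% and 50% are assumed, to show the effect of recruitment).

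**Step 5, what splitting costs in precision.** If no event is seen in n subjects, the one-sided 95% upper bound is 1 − 0.05^(1/n): 2.0% for n = 150, 3.0% for n = 100, 5.8% for n = 50. SAP section 6 sets no size requirement beyond the primary objective, so a split disturbs no powered analysis.

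**The case against.** The fair case for the plan is that this is a descriptive, single-arm, post-market study with no safety hypothesis. Further division of the cohort is expressly permitted, and CIP 4.2 promises sub-group analyses of characteristics related to outcomes. The Additional Measures text is not visible, so lesion-level safety detail may exist there. All of that stands as far as it goes, and it rules out saying that such figures can never be obtained. None of it is a visible commitment to safety tables by lesion group, and the sections that govern those tables stop at the cohort.

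Two stronger readings are tempting.

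- *That benign subjects dilute the harms seen in metastatic subjects.* The documents give no event rate by lesion group for this device. The opposite is possible: benign tumours may be treated at any location, and the warnings in CIP 10.2.1 describe pathologic fracture as commoner and more serious in long bone.
- *That benign subjects inflate pain relief for non-vertebral metastatic subjects.* SAP 7.9.2 does say: "The main analysis for the secondary objective will be on the Secondary Objective Cohort and will use the Completers Analysis Set". But both documents also commit to the separate lesion-group pain results, CIP 13.4.6 reports the Treated and Completers populations, and SAP 7.9.2 adds sensitivity analyses on the Treated set. The objective is descriptive, so which figure is called main is a matter of presentation. The osteoid osteoma series in CIP 4.4, with complete symptom resolution in the 16 patients followed beyond 30 days, was retrospective, used another ablation system and included children. It cannot settle the size of any difference here.

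**Conclusion.** The point holds for safety and only for safety. The visible plan commits to no adverse event or device deficiency table for non-vertebral metastatic subjects or for benign-tumour subjects, two of the three groups for which it sets enrolment goals. The pooled percentage is from 33% too low to 17% too high for the metastatic group over assumed risk ratios of 0 to 1.5. It is exact only if the two risks are equal. Those figures rest on the planned 100 and 50, no combination subjects, equal treated fractions, and a risk ratio that the documents do not supply. The direction is unknown, and the case for the change does not need it.

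A reader might infer that the secondary pain result has the same gap. It does not, because the lesion-group pain results are already required. The safety tables merely lack the breakdown that the pain analysis has. This is an inexpensive improvement to an otherwise workable safety plan.

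**What to change.** In SAP 7.10 and CIP 13.5.2, state that adverse event and device deficiency tables will be given for four groups, alongside the aggregate: vertebral-only metastatic (already the Primary Objective Cohort), non-vertebral metastatic, benign, and combinations. Use the same group definitions as the pain analysis in CIP 13.4.6 and SAP 7.9.2.

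No new data are needed: treated-site location is recorded at the procedure, and cohort assignment already depends on the lesion types treated. The cost is a few table shells and smaller denominators. With no events, the upper bound for the benign group would be 5.8% on 50 subjects, against 2.0% for the pooled 150. The combination group may be very small and may be better shown as counts or a listing than as percentages.
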